Eligibility Criteria	
Inclusion criteria
 
 
1. Term pregnancy
 
2. Age 18-45 years of age
 
3. Scheduled cesarean delivery under neuraxial anesthesia
 
 
Exclusion criteria
 
 
1. ASA classification IV or V
 
2. History of psychotic episodes
 
3. History of allergy to ketamine
 
4. Inability to communicate in English or any other barrier to providing informed consent
 
												
Measurements	
 
Psychosocial stress (Antenatal Risk Questionnaire [ANRQ])
 
Weight (kg) and height (m)
 
Time of delivery of baby
 
Total intraoperative dose of analgesic/sedative medication
 
Baseline and intraoperative vital signs
 
Maximum intraoperative pain (NRS)
 
48-hour total opiate consumption (morphine equivalents)
 
Apgar scores at 1 and 5 minutes postpartum
 
Admission to NICU
 
												

	
 
j) Pain originating from surgical site (NRS 0-10): 2, 6, 24 and 48 hours and 21 and 42 days postpartum.
 
k) Edinburgh Postpartum Depression Scale (EPDS) and Generalized Anxiety Disorder 7-item (GAD-7) Scale: Day of surgery and postpartum days 1, 2, 21 and 42
 
l) Plasma concentrations of ketamine at baseline, 20, 40 and 100 minutes after administration
 
m) Breastfeeding success (Y/N): postpartum days 1 and 2
 
n) Adverse effects, intraoperatively and at 2 and 6 hours postpartum (absent, mild, moderate or severe)
 

Statistical Methodology	
Descriptive statistics will be employed to present the demographic data. Continuous variables will be summarized using means (SD) or medians (IQR), as appropriate. After construction of the concentration-time curves for each patient, the peak plasma concentration and area under the concentration-time curve will be summarized overall and associations with both antidepressant effect and incidence of adverse symptoms will be explored.
 
NONMEM® 7.4 (ICON Development Solutions) software will be utilised to assess pharmacokinetic profile of ketamine by each route.

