### 1.3 Ketamine and PPD

This promising anti-depressant effect has prompted investigation of ketamine as a preventative measure in patients undergoing CD. There have been 2 studies to date, one which failed to demonstrate any benefit from a bolus dose of 0.25 mg/kg and one which documented a large reduction (1 and 22% in the treatment and control, respectively) in the (6 week) period prevalence of postpartum depression after a 4 mg/kg dose of ketamine over 50 hours (~0.08 mg/kg/hr).

The prolonged IV infusion, in the Jianxin (2015) study, was achieved by adding the ketamine to a sufentanil patient-controlled analgesic (PCA) pump with a background infusion. This PCA pump is a standard part of their post-cesarean analgesic regimen. In our institution, it is standard practice to discontinue IV infusions and to remove IV cannulae as early as it is safe to do so. This practice is essential to the attempts to enhance postoperative recovery and aid mother's bonding with their babies and facilitate their early-

life care. This reflects patients' expectations and preferences and is in line with other maternity units across North America and Europe.

The natural course of PPD varies and, although it may resolve spontaneously within weeks, approximately 20% of women with PPD still have depression at 12 months and beyond. As many as 13% will still have depressive symptoms at 2 years and 40% will have a relapse. Considering the maternal suffering, disruption to the family, potential impairment of the social, emotional, and cognitive development of the child, and the rare cases of infanticide and suicide caused by PPD, the impact on families and society as a whole is difficult to overemphasize. An intervention that promises such a large reduction in this devastating disease warrants extensive research. In an attempt to achieve the benefit demonstrated by Jianxin et al. whilst employing methods more acceptable to our patients we have designed a pilot study to assess the feasibility of our study design and collect preliminary tolerability and efficacy data on ketamine administered by two alternative routes: 40-minute IV infusion (i.v.) and subcutaneous (s.c.) injection.

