## 2 OBJECTIVES

- 2.1 To determine the feasibility of performing this study at our institution
- 2.2 To determine the pharmacokinetic profiles of ketamine when administered as a subcutaneous injection and an intravenous infusion at cesarean delivery
- 2.3 To obtain preliminary data to inform the design of a randomized controlled trial to assess the efficacy of ketamine as a preventive intervention at cesarean delivery against PPD

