## 6 STUDY PROCEDURES

6.1 Participants will be assigned to one of three intervention groups (Table 2).

Groups	Subcutaneous injectate	Intravenous injectate*
SC (n=20)	50 mg/ml ketamine	0.9% Sodium Chloride
IVI (n=20)	0.9% Sodium Chloride	50 mg/ml ketamine
P (n=20)	0.9% Sodium Chloride	0.9% Sodium Chloride

**Table 2:** Intervention groups. \*the i.v. injectate will be diluted up to a 40 ml infusion.

6.2 Participants will have baseline data (Table 3) recorded on the relevant case report form on the day of delivery. This data will include demographics to assess the performance of randomization procedures as well as characteristics that have been demonstrated to confer an increased risk of PPD. The patient will be prepared for cesarean as per institutional protocols.

Measure	Units/values
Age	Years
Height	Metres
Weight (day of surgery)	Kilograms
Gestational age	Weeks
Ethnicity	White, Black/African American, Asian, Native American/Alaskan natives, Native Hawaiian, Pacific Islander, Hispanic/Latino
Insurance status	Insured/uninsured
Psychiatric history	PPD, major depressive disorder (MDD), anxiety, premenstrual syndrome (PMS), premenstrual dysphoric disorder (PMDD), mood disorder, personality disorder, psychotic disorder
Current anxiety and depressive symptoms	EPDS and GAD-7
Psychosocial stress	ANRQ

**Table 3:** Baseline data

Once an adequate sensory block is achieved, surgery will commence. Upon delivery of the baby, 0.01 ml/kg of the “*subcutaneous injectate*” will be injected subcutaneously and the “*intravenous injectate*” will be made up to a 40ml infusion (Table 4) and commenced at 60 ml/hr. Both injectates will be administered/initiated approximately 0 - 5 minutes after delivery by the anesthetic provider via one of the cannulae that they will be using for standard patient care. The intravenous study infusion will be prepared by a member of the investigative team, who will not be involved in data collection.

---

Add 0.01 ml/kg of the “*IVI study solution*” to a 60ml syringe and use 0.9% sodium chloride to dilute the solution to 40ml.

---

**Table 4:** Instructions for preparing the “*IVI study infusion*”

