### 8.2 Secondary outcome measures

- 8.2.1 Intraoperative supplementary analgesia
- 8.2.2 Intraoperative hypo/hypertension and brady-/tachycardia
- 8.2.3 Maximum intraoperative pain (NRS)
- 8.2.4 Adverse effects intraoperatively and at approximately 2 and 6 hours postpartum
- 8.2.5 Plasma concentrations of ketamine at baseline and approximately 20, 40 and 100 minutes postpartum. Samples will be centrifuged and the extracted plasma samples will be stored at -80 degrees Celsius before transfer to the metabolomics laboratory at Washington University for ketamine assay.
- 8.2.6 Total opiate consumption in the first 2 days postpartum
- 8.2.7 Surgical site pain (NRS 0-10), by face-to-face or telephone interview, at 2, 6, 24 and 48 hours after delivery and on postpartum days 21 and 42.
- 8.2.8 EPDS and GAD-7 on postpartum days 1 and 2, by face to face interview, and days 21 and 42, by telephone interview.
- 8.2.9 Apgar scores
- 8.2.10 Admission to NICU
- 8.2.11 Breastfeeding success (Y/N) on post-operative days 1 and 2

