## 9 STATISTICAL METHODS

### 9.1 Sample size and analysis

No formal sample size has been performed as this is a pilot designed to establish the feasibility of an RCT. Preliminary data from this study will be used to inform the sample size calculation for the subsequent clinical trial. Descriptive statistics will be employed to present the demographic data. Continuous variables will be summarized using means (SD) or medians (IQR), as appropriate. After construction of the concentration-time curves for each patient, the peak plasma concentration and area under the concentration-time curve will be summarized overall and associations with both antidepressant effect and incidence of adverse symptoms will be explored.

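### Ketamine sampling stops at about 100 minutes, so the per-patient AUC is truncated in a way that depends on input rate, and clearance and total exposure are weakly supported

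*Combined protocol and SAP*

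**What the plan says.** Objective 2.2 is "To determine the pharmacokinetic profiles of ketamine when administered as a subcutaneous injection and an intravenous infusion at cesarean delivery". The Synopsis hypothesis adds that the subcutaneous route has a favorable pharmacokinetic profile.

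Section 8.2.5 lists "Plasma concentrations of ketamine at baseline and approximately 20, 40 and 100 minutes postpartum". Section 6 (Measurements, item 11) and the blood-sample row of Table 6 agree, and no later pharmacokinetic draw is scheduled. The Synopsis counts time from a different origin: "Plasma concentrations of ketamine at baseline, 20, 40 and 100 minutes after administration". Section 6 says "Both injectates will be administered/initiated approximately 0 - 5 minutes after delivery", so the two clocks can differ by up to about 5 minutes.

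Section 9.1 constructs a concentration-time curve for each patient, after which "the peak plasma concentration and area under the concentration-time curve will be summarized overall" and related to antidepressant effect and adverse symptoms. It gives no AUC window, integration method or extrapolation rule. Section 9.2 adds a NONMEM analysis by route without naming a model.

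**The concern.** Each treated patient contributes three post-dose concentrations, of which only the 100-minute one lies clearly after the infusion. If dosing starts 5 minutes after delivery, a 40-minute sample timed from delivery falls before the infusion ends. One late point cannot define a patient's elimination phase.

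The AUC in section 9.1 is thus an AUC over roughly 0-100 minutes. Over so short a window, two routes that deliver the same total exposure can give different AUCs because drug enters at different speeds. Pooling them overall mixes exposure with input rate, and the mixture carries into the planned exploration against antidepressant effect and adverse symptoms. The fourth draw is taken before dosing, when study ketamine is absent, so it adds almost nothing to the profile.

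**Working it through.** **Inputs from the documents.** Section 6 gives "0.01 ml/kg of the" injectate by either route, at "50 mg/ml ketamine": 0.01 × 50 = 0.5 mg/kg in both ketamine arms. The infusion is 40 ml at 60 ml/hr: 40/60 h = 40 min, which reproduces the 40-minute infusion stated in section 1.3. There are 20 patients per arm, so 40 receive ketamine.

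**Assumptions (not in the documents).** One compartment; elimination half-life 1-4 h; first-order subcutaneous absorption with half-time 5-45 min; complete bioavailability; linear trapezoid at 0, 20, 40 and 100 min, because section 9.1 names no method.

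**Formulas** (dose/volume = 1, k = ln 2/half-life, ka = ln 2/absorption half-time, T = 40 min):
- Intravenous, t ≤ T: C = (1 − e^(−kt))/(kT). For t > T: C = C(T)·e^(−k(t−T)).
- Subcutaneous: C = ka/(ka − k)·(e^(−kt) − e^(−ka·t)).
- Total AUC = 1/k for both routes, so the true ratio is 1.00.

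**Worked case, 2 h half-life** (1/k = 173.1):
- Intravenous concentrations 0, 0.472, 0.893, 0.631. AUC = 4.72 + 13.65 + 45.73 = 64.10, which is 64.10/173.1 = 37% of the total.
- Subcutaneous, 45 min absorption: 0, 0.250, 0.406, 0.555. AUC = 2.50 + 6.56 + 28.83 = 37.88. Ratio 37.88/64.10 = 0.59.
- Subcutaneous, 10 min absorption: 0, 0.699, 0.798, 0.611. AUC = 6.99 + 14.97 + 42.27 = 64.23. Ratio 1.00.

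**Full range, 0-100 min:**

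| Half-life | Intravenous AUC captured | Ratio, 5 min | 10 min | 20 min | 45 min |
|---|---|---|---|---|---|
| 1 h | 61% | 1.01 | 0.97 | 0.84 | 0.59 |
| 2 h | 37% | 1.06 | 1.00 | 0.85 | 0.59 |
| 3 h | 26% | 1.07 | 1.01 | 0.86 | 0.59 |
| 4 h | 21% | 1.08 | 1.02 | 0.86 | 0.59 |

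A two-compartment check over absorption half-times of 5-40 min gave 0.60-0.91, and 0.88-0.91 at 10 min. The near-absence of bias at 10 min therefore belongs to the one-compartment case.

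**Population model.** A first-order Fisher information calculation used 20 intravenous and 20 subcutaneous patients. Assumed values: one compartment, half-life 2-4 h, absorption half-time 10-40 min, bioavailability 0.8, between-patient SD 0.3 (clearance, volume), 0.4 (absorption rate) and 0.2 (bioavailability), residual SD 0.2 on the log scale.

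| Relative standard error | 20/40/100 min | 20/40/100/360 min |
|---|---|---|
| Clearance | 13-27% | 6-8% |
| Relative bioavailability | 10-13% | 9-10% |

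These errors are optimistic: fixed effects only, one compartment, exact sampling times.

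**Trapezoid with a 360-minute sample.** It returns 124%, 95%, 77% and 65% of total intravenous AUC at half-lives of 1, 2, 3 and 4 h. The long 100-360 min interval makes it overshoot at 1 h. The ratio narrows to 0.82-1.00 but still depends on absorption rate.

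**The case against.** A reader might infer that the design cannot compare the two routes. The documents do not support that. Section 9.2 plans a NONMEM analysis, which can pool sparse samples from 40 treated patients; on the existing three post-dose samples it would estimate relative bioavailability with a relative standard error of about 10-13% under the assumptions above. Nor does objective 2.2 ask for a comparison of total exposure: it asks for the profile by each route, and section 9.1 proposes no route ratio.

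A reader might also infer that the AUC mostly reflects how early drug appears. That is not shown. It depends on an absorption rate that the documents do not give; the 0.59 arises only at the slow end of the assumed range, and how much patients' AUCs would vary was not computed. Early exposure is also relevant in its own right to adverse effects recorded during surgery and at 2 hours.

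The pre-dose draw has some value, since it gives each patient her own blank, which placebo plasma from other women cannot. A 6-hour draw also carries a burden, because at this institution "it is standard practice to discontinue IV infusions and to remove IV cannulae as early as it is safe to do so".

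All of this stands, and it limits the point. It does not remove the truncation, the missing AUC definition or the weak information on clearance.

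**Conclusion.** The concern holds in limited form. With sampling ending at about 100 minutes, the AUC in section 9.1 is truncated and sensitive to input rate, and clearance and total exposure are weakly supported for the profiles in objective 2.2. Under the stated one-compartment assumptions the AUC captures about 21-61% of intravenous exposure, and equal true exposure can appear as a subcutaneous:intravenous ratio anywhere from 0.59 to 1.08. A model-based route comparison is imprecise for clearance but not impossible, and a late sample would improve its bioavailability estimate only slightly. Every size quoted rests on assumed pharmacokinetic values. The point concerns a secondary outcome, not the design of the feasibility milestones; it is worth acting on because the remedy is cheap.

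**What to change.** 1. **Sampling.** In 8.2.5, Section 6 item 11 and Table 6 (and the matching Synopsis line), replace the pre-dose ketamine draw with one at the 6-hour contact, which already exists for pain and adverse effects. Do this in all arms so that blinding is kept. The 20 × 3 = 60 placebo-arm samples at 20, 40 and 100 minutes serve as assay blanks.
2. **AUC.** In 9.1, label the observed value AUC(0-100 min), report it by route rather than only overall, and state that it is not total exposure. Take total exposure from the NONMEM fit only if the late sample is added. Without it, that figure rests on the parameter most weakened by the missing late data, and individual estimates shrink toward the population mean. Do not use a linear trapezoid across 100-360 minutes for this purpose.
3. **Specification.** Name the NONMEM model in 9.2, and reconcile the time origin (delivery or administration) between the Synopsis and sections 6 and 8.2.5.

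**Cost.** A short amendment with no added draws or contacts. The 6-hour draw may need a venepuncture, each patient loses her own pre-dose blank, and some draws may be missed. FM3 needs a complete dataset in more than 90% of participants: 0.9 × 60 = 54, so at least 55 must be complete and six missed draws could fail it on their own. The sponsor should state whether this draw counts toward FM3. If the late draw is declined, the labelling and by-route reporting in item 2 still apply.

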## 9 STATISTICAL METHODS

### 9.1 Sample size and analysis

No formal sample size has been performed as this is a pilot designed to establish the feasibility of an RCT. Preliminary data from this study will be used to inform the sample size calculation for the subsequent clinical trial. Descriptive statistics will be employed to present the demographic data. Continuous variables will be summarized using means (SD) or medians (IQR), as appropriate. After construction of the concentration-time curves for each patient, the peak plasma concentration and area under the concentration-time curve will be summarized overall and associations with both antidepressant effect and incidence of adverse symptoms will be explored.

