## SYNOPSIS

Study Title	Postpartum depression after Cesarean delivery: Ketamine as a preventative intervention. A feasibility pilot-study (PoCKet Pilot).												
Primary Objective	To assess the feasibility of the study by establishing: a) the incidence of PPD in our cohort; b) the acceptability to eligible patients; c) the ability of the investigative team to collect the data and; d) the tolerability of the interventions.												
Hypothesis	We hypothesize that ketamine reduces the incidence of postpartum depression (PPD) when administered at cesarean delivery and that the subcutaneous route is well tolerated and has a favorable pharmacokinetic profile.												
Study Period	Planned enrolment duration: 52 weeks Planned study duration: 58 weeks												
Number of Participants	60 patients (20 in each of the subcutaneous [SC], intravenous [IVI] and control [P] groups)												
Study Intervention	Patients in each group will receive both subcutaneous (s/c) and intravenous (i.v.) administration of their corresponding injectate shortly after delivery of their baby. The injectate will consist of either 0.9% Sodium Chloride (N/S) or 50 mg/ml ketamine (Ket) depending on their group allocation. The s/c injectate will be administered undiluted whereas the i.v. injectate will be diluted to make up a 40 ml infusion. 
  
 Groups	s/c injectate	i.v. injectate	
   
 SC:	Ket	N/S	
 
 IVI:	N/S	Ket	
 
 P:	N/S	N/S	
  
	Groups	s/c injectate	i.v. injectate	SC:	Ket	N/S	IVI:	N/S	Ket	P:	N/S	N/S
Groups	s/c injectate	i.v. injectate											
SC:	Ket	N/S											
IVI:	N/S	Ket											
P:	N/S	N/S											
Study Design	A randomised, double-blind, placebo-controlled feasibility pilot study												

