### Measurements:

1. Baseline data
2. EPDS and GAD-7 scores at baseline and approximately 1, 2, 21 and 42 days postpartum

3. ANRQ at baseline
4. Time of delivery of baby
5. Total intraoperative dose of any analgesic/sedative medication
6. Incidence of hypo- or hypertension (systolic BP < 80 or > 170 mmHg, respectively) and brady- or tachycardia (pulse < 40 or > 120 bpm, respectively)
7. Maximum intraoperative pain (numerical rating scale [NRS], 0-10)
8. Incidence of the signs/symptoms in Table 5 will be assessed intraoperatively and approximately 2 and 6 hours after delivery. The presence of each adverse effect will be assessed using a 4-point scale (absent, mild, moderate, severe).

Nausea	Shivering	Blurred vision
Vomiting	Anxiety	Diplopia
Pruritus	Euphoria	Nystagmus
Dizziness	Hallucinations	
Sedation	Amnesia	

**Table 5:** Adverse effects

9. Surgical site pain (NRS) at 2, 6, 24 and 48 hours, as well as 21 and 42 days, postpartum.
10. Opiate consumption in the first 48 hours (measured in morphine equivalents) will be calculated.
11. Plasma concentrations of ketamine at baseline and approximately 20, 40 and 100 minutes postpartum.

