## 7 STUDY SCHEDULE

Study Event	Baseline	Perioperative (approximate minutes after delivery)			Postoperative (approximate hours after delivery)				Outpatient (approximate days after delivery)	
		20	40	100	2	6	24	48	21	42
Informed consent	✓									
Eligibility/ Demographics	✓									
Randomization	✓									
Blood Sample Collection	✓	✓	✓	✓						
Maximum intraoperative pain (NRS, 0-10) score					✓					
Adverse Effects				✓	✓	✓				
Breastfeeding Success							✓	✓		
Surgical Site Pain (NRS)					✓	✓	✓	✓	✓	✓
EPDS	✓					✓	✓	✓	✓	✓
GAD 7	✓					✓	✓	✓	✓	✓
ANRQ	✓									

**Table 6:** Study schedule

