### 9.2 Pharmacokinetic analysis

NONMEM® 7.4 (ICON Development Solutions) software will be utilised to assess pharmacokinetic profile of ketamine by each route.

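### Section 9.1 pools ketamine Cmax and AUC across arms with no route term, and the sampling clock starts at dosing in one place and at delivery in three others

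*Combined protocol and SAP*

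**What the plan says.** **Summary and association.** Section 9.1 builds a concentration-time curve for every patient and states that "peak plasma concentration and area under the concentration-time curve will be summarized overall". It then explores associations with antidepressant effect and adverse symptoms. The synopsis repeats this. Neither place gives a by-route summary, a restriction to ketamine recipients or a model.

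**What is framed by route or arm.** The synopsis hypothesis is that "the subcutaneous route is well tolerated and has a favorable pharmacokinetic profile". Objective 2.2 asks for the profile of each route, and milestone FM4 is judged within each arm. Section 9.2 adds that NONMEM "software will be utilised to assess pharmacokinetic profile of ketamine by each route". It does not mention Cmax, AUC or exposure-response.

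**Sampling times.** Item l of the synopsis measurements reads "Plasma concentrations of ketamine at baseline, 20, 40 and 100 minutes after administration". Section 8.2.5 reads "Plasma concentrations of ketamine at baseline and approximately 20, 40 and 100 minutes postpartum", and item 11 of the Section 6 measurement list uses the same origin. Table 6 in Section 7 heads the sampling columns "Perioperative (approximate minutes after delivery". Section 6 separates the two origins: "Both injectates will be administered/initiated approximately 0 - 5 minutes after delivery". The measurement lists include "Time of delivery of baby" but no time of injection, of infusion start or stop, or of any blood draw.

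**The concern.** A pooled Cmax or AUC describes neither route if the routes differ, and the pilot's PK question is about routes. If saline patients are counted, a third of the values are about zero.

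The association step carries more risk. When exposure and outcome both differ between arms, a pooled correlation can arise from arm membership alone, with no relation between concentration and outcome inside any arm. The pilot is meant to inform a later trial, so such a result could be taken as evidence about concentration.

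The clock matters because the first sample is early. If nominal times were treated as time since dosing, the error would vary with each patient's delay, and it would differ between an infusion still running and an injection being absorbed. A time not recorded on the day may not be recoverable.

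**Working it through.** **Inputs from the protocol**
- Arms: 3 × 20 = 60, of which 20 receive saline only (synopsis; Table 2).
- Infusion: 40 ml at 60 ml/hr (Section 6), so 40/60 × 60 = 40 minutes. This reproduces the 40-minute infusion named in Section 1.3.
- Dose in either ketamine arm: 0.01 ml/kg × 50 mg/ml = 0.5 mg/kg.
- Nominal samples at 20, 40 and 100 minutes; dosing about 0 to 5 minutes after delivery.
- Section 9.1 has no formal sample size, so there is no power figure to reproduce.

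**Assumptions (not in the protocol).** One compartment; elimination half-life 60 to 180 minutes; subcutaneous (SC) absorption half-life 5 to 30 minutes; full SC bioavailability unless stated. Let k and ka be ln 2 divided by these half-lives.

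**Step 1: pooled summary.** Per unit dose/volume:
- Intravenous (IV) Cmax = (1 − e^(−40k)) / (40k).
- SC Cmax = (ka/k)^(−k/(ka−k)).

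Example with half-lives of 60 (elimination) and 30 (absorption) minutes: IV = 0.370/0.462 = 0.801, SC = 2^(−1) = 0.500, ratio 0.62. Over the whole grid the SC/IV ratio is 0.62 to 1.00 for Cmax and 0.77 to 1.14 for AUC from 0 to 100 minutes.

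At ratio 0.62, the mean over ketamine recipients is (1 + 0.62)/2 = 0.81 of the IV mean and 0.81/0.62 = 1.30 times the SC mean. At ratio 1.00 pooling does no harm. With an assumed SC bioavailability of 0.5, the pooled mean is 0.66 to 0.75 of IV and 1.5 to 2.1 times SC. Counting 20 placebo zeros multiplies any active-arm mean by 40/60 = 2/3.

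**Step 2: association.** 5,000 simulated trials per setting, 20 per arm, log-normal exposure with CV 0.3 to 0.5, and the adverse symptom drawn independently of exposure within each arm. The test is a Pearson correlation, or a within-route partial correlation on 37 df.

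| Patients analysed | Assumed symptom rates | SC/IV Cmax ratio | p<0.05, no route term | p<0.05, route term |
|---|---|---|---|---|
| All 60 | placebo 10%, ketamine 30% | 1.0 | about 24–33% (mean r 0.17–0.20) | – |
| All 60 | placebo 10%, ketamine 50% | 1.0 | about 67–82% (mean r 0.31–0.35) | – |
| All 60 | placebo 10%, ketamine 50% | 0.62 | about 60–76% | – |
| 40 recipients | equal in both routes | 0.62 or 1.0 | about 5% | about 5% |
| 40 recipients | IV 50%, SC 20% | 0.62 | 14–24% | 5–7% |
| 40 recipients | IV 50%, SC 20% | 1.0 | about 5% | about 5% |

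A separate simulation with a continuous outcome (4,000 runs per setting, CV 40%, Cmax ratio 0.5 to 1.0) agrees. A ketamine effect of 0.5 to 0.8 SD, common to both routes and unrelated to concentration within arm, gives p<0.05 in 27% to 64% of runs over all 60, and about 5% in the 40 recipients. With an effect of 0.8 SD in the IV arm only and ratio 0.5, the 40 recipients without a route term still give 32%. Restricting the analysis set is therefore not enough when the routes differ in both exposure and outcome.

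**Step 3: clock.** A sample labelled t after delivery is taken t − d after dosing starts. During the infusion the concentration is proportional to 1 − e^(−kt), so the relative error is (1 − e^(−k(t−d))) / (1 − e^(−kt)) − 1.

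For t = 20, d = 5:
- half-life 60: 0.1591/0.2063 − 1 = −23%
- half-life 180: 0.0561/0.0741 − 1 = −24%

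| Delay | 20-min IV | 40-min IV |
|---|---|---|
| 1 min | −5% | −2% |
| 2.5 min | −11 to −12% | −5 to −6% |
| 5 min | −23 to −24% | −10 to −12% |

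At 5 minutes the SC values change by −2 to −20% (20 min) and −7 to +5% (40 min). The 100-minute values change by 0 to +6% on both routes. Trapezoidal AUC to 100 minutes changes by about −9% (IV) and −6 to +3% (SC).

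**The case against.** **Route is already covered.** Objective 2.2 and the by-route NONMEM analysis address route-specific PK, and an overall summary does not forbid by-route summaries. This narrows the point to the Cmax/AUC summary and the association step. Section 9.2 mentions neither, so the gap there remains.

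**Placebo would not be included.** Saline patients have no real ketamine curve, the text does not say that they are counted, and the largest figures depend on counting them. With randomised controls, the pooled correlation would also reflect a real drug effect; it misleads only if read as a graded concentration effect. All of this is fair. Yet curves for each patient, summarised overall, literally take in all 60, and the sampling schedule is not limited to the ketamine arms.

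**The ketamine-only harm needs large differences.** With IV and SC symptom rates of 50% and 20%, the pooled rate of p<0.05 falls to about 8–12% at a Cmax ratio of 0.8 and 6–7% at 0.9. With rates of 40% and 30% it is about 7% even at 0.62. The plan also specifies no test or decision for these associations. This stands: the size is conditional, and p<0.05 serves here only as a yardstick.

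**The clock gap is small.** It is at most about 5 minutes, and the times from delivery are stated as approximate. At 2.5 minutes the sampled AUC moves by about −4% (IV) and −3 to +2% (SC). The case report forms are not in the document and may hold actual times. That also stands, but the contradiction in origin is real and the plan does not say which time is analysed.

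**Conclusion.** The concern holds on both counts. As written, the Cmax/AUC summary and the exposure-response exploration are pooled, and the sampling origin is stated in two incompatible ways.

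The harm from pooling the summary over ketamine recipients runs from none to about 30% relative to the SC mean at full bioavailability, and is larger if bioavailability is lower. A spurious association is likely if placebo values are included and ketamine changes the outcome. Among recipients alone, it arises only when the routes differ clearly in both exposure and outcome. The clock error is modest for AUC but reaches about a quarter of the 20-minute IV value at the edge of the dosing window, and only if nominal times are used as time since dosing.

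All PK values, symptom rates and effect sizes here are assumptions. The four feasibility milestones are unaffected. The change is worth making because it is cheap and because dosing and draw times must be captured on the day. Confidence in the size is moderate.

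**What to change.** 1. In Section 9.1 and the synopsis, replace the overall summary with Cmax and AUC summarised separately for the SC and IVI groups among ketamine recipients. State the AUC window, for example 0 to 100 minutes to match the last sample. Use placebo samples only as a check for zero.
2. Explore associations of exposure with EPDS and with adverse effects within the two ketamine arms, with a route term, and label them exploratory.
3. Reconcile the synopsis (item l), the Section 6 measurement list (item 11), Table 6 and Section 8.2.5 on one sampling origin.
4. Add the actual times of subcutaneous injection, infusion start and stop, and each draw to the measurement list. State in Sections 9.1 and 9.2 that the curves and NONMEM use actual time since the start of dosing.

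The cost is a few sentences and, if not already present, a few case report form fields, with no extra samples or patients. The downside is that each summary rests on 20 women and the association step on at most 40.
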